## STUDY SYNOPSIS

Title	A Pilot Study of iTBS in Bipolar I Depression
Source of Funding	Baszucki Brain Research Fund
Study Population	Participants aged 18+ years old with a diagnosis of bipolar I disorder, current episode depressed
Study Design	A multisite, open label pilot study to investigate the efficacy and safety of a novel accelerated intermittent theta-burst stimulation (iTBS) protocol while assessing for changes in neuroimaging biomarkers associated with treatment response
Primary Objectives	To examine the use of accelerated iTBS to treat symptoms of treatment resistant depression in bipolar I disorder and assess changes in neuroimaging biomarkers that may predict treatment response.
Number of Sites	2
Total number of Participants	10 (5 at each site)
Study Duration	1 year

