### **Follow-up [Day 8-40]:**

Due to COVID-19 or related considerations, we will perform follow-up assessments via a secure audio/video platform in cases where we cannot conduct in-person assessments or per participant preference.

For participants completing treatment prior to the 5-day period, immediate post-treatment evaluation is defined as up to 5 days after the last day of treatment and 1-month post-treatment evaluation is defined as 25-35 days after the last day of treatment.

Participants will have the same clinical and neurocognitive assessments that were completed during the baseline time-period at the immediate post-treatment and 1-month post-treatment mark. In addition, we will also administer the CGI-BP at these 2 time points.

Participants will complete the following self-report assessments at these two follow-up time points as long as they meet responder/remission criteria:

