## **9. STATISTICAL CONSIDERATIONS**

### **9.1 General Design Considerations**

This is an open label pilot study. The study will not include blinding given that this is a single group assignment to treatment. Study will not include a placebo or non-treatment group as this is a feasibility pilot study.

The sample size for this pilot study was selected to allow for a sufficient evaluation of the feasibility of carrying out the protocol across multiple NNDC centers given the available resources and provide preliminary data to motivate further study of this treatment approach.

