### **9.3 Outcomes**

#### **9.3.1 Primary Outcome**

The primary outcome measures for this study will be change in MADRS scores. The MADRS is a clinical assessment tool used to rate a patient's level of depression and is the standard scale used for depression research studies. The YMRS will be used as a second primary outcome measure to assess any changes in symptoms of mania over the course of treatment. The YMRS is a clinical assessment tool used to assess the presence and severity of manic symptoms. The primary outcome measures will be assessed as the change between baseline and immediate (up to 5 days after last day of treatment) post-treatment assessment.

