## 9.4 Data Analyses

The primary outcome measures will be analyzed using generalized linear mixed models to test if there are significant changes in scores over follow-up. Based on previous work, we will use a compound symmetry or autoregressive covariance structure (based on distribution of residuals) and robust estimation of coefficients to handle violations of model assumptions. Random effects will be included to account for repeated measures on the same participants, and fixed effects of time will be evaluated controlling for fixed effects of age, sex and number of days to reach treatment remission. All post hoc pairwise comparisons will be Bonferroni corrected. Exploratory endpoints related to biometrics will be analyzed in similar fashion.

For assessment of the secondary outcome measures of change in functional connectivity, we will employ a resting-state seed-based functional connectivity approach to assess connectivity between the subcallosal cingulate connectivity to the DLPFC and within the default mode network. For each participant, the correlation coefficients between average blood oxygen level-dependent (BOLD) time series of the seed-region and the BOLD time series of each grey matter voxel within the DLPFC or default mode network will be calculated. The correlation coefficient will be converted to normally distributed z scores by the application of Fisher's r to z transformation. The resulting connectivity maps will be analyzed with repeated measures ANOVA to compare pre-iTBS vs post-iTBS connectivity measures as a within-subject variable, and sex and site as a between-subject covariate.

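### Section 9.4 Bonferroni-corrects post hoc comparisons of the YMRS, a harm outcome, over an undefined family, which weakens the reported mania and depression time courses

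*Combined protocol and SAP*

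**What the plan says.** Section 9.3.1 names two primary outcomes. The MADRS is the first, and "The YMRS will be used as a second primary outcome measure to assess any changes in symptoms of mania over the course of treatment". For both, the primary assessment is a single contrast: the "change between baseline and immediate (up to 5 days after last day of treatment) post-treatment assessment".

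Section 9.4 covers both outcomes with generalized linear mixed models that "test if there are significant changes in scores over follow-up". In these models "fixed effects of time will be evaluated controlling for fixed effects of age, sex and number of days to reach treatment remission". The multiplicity rule is one sentence: "All post hoc pairwise comparisons will be Bonferroni corrected". Section 9.4 does not state alpha or sidedness, which ratings enter the model, which pairs count as post hoc, or whether the YMRS is treated differently from the MADRS.

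Section 6.2 has the YMRS and MADRS rated morning and evening on up to five treatment days. Both are also rated at baseline, and participants have the "same clinical and neurocognitive assessments that were completed during the baseline time-period at the immediate post-treatment and 1-month post-treatment mark". The sample is 10 participants, five per site. Section 9.1 explains the number this way: "The sample size for this pilot study was selected to allow for a sufficient evaluation of the feasibility".

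**The concern.** Family-wise correction guards against false claims of benefit. On a harm outcome it works the other way, because it makes a rise in symptoms harder to call a rise. The synopsis says the study investigates safety as well as efficacy, and Section 7 lists induction of mania as a risk.

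The primary contrast runs from baseline to the immediate follow-up. If mania emerges, treatment stops and the symptoms are treated (Sections 6.2 and 7.2), so a rise in mid-course may have settled by that visit. The comparisons of treatment-day ratings with Day 0 would show when such a rise occurred, and these are the ones the correction reaches.

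Because the family is undefined, the size of the penalty is undefined too. If every pair of ratings counts, comparisons that answer no clinical question, such as Day 2 evening against Day 4 morning, tighten the threshold for those that do. The same applies to the MADRS when the report asks how early improvement starts and whether it lasts.

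**Working it through.** The plan states no alpha, power or corrected threshold, so there is no figure of its own to reproduce.

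**Inputs from the documents.** n = 10. Ratings: Day 0, 5 × 2 = 10 on treatment days, and 2 at follow-up, which makes 13.

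**Assumptions.** Two-sided alpha of 0.05; complete data; effect d = true mean change divided by the SD of change.

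**Family size and threshold (0.05/k).**
- Change from Day 0 only: k = 12, threshold 0.05/12 = 0.0042.
- One rating per treatment day plus Day 0 and two follow-ups (8 ratings), all pairs: k = 8 × 7/2 = 28, threshold 0.0018.
- All 13 ratings, all pairs: k = 13 × 12/2 = 78, threshold 0.00064.

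**Power.** Noncentral t with noncentrality d√10, at alpha 0.05/k. Two choices of degrees of freedom bracket the analysis: 9 (paired t-test, 10 − 1) and 108 (a mixed model using all ratings, (10 − 1) × (13 − 1)).

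| Family | Critical t (9 df) | Smallest significant mean, critical t/√10, in SD | Power d=1, 9 df | Power d=1.5, 9 df | Power d=1, 108 df | Power d=1.5, 108 df |
|---|---|---|---|---|---|---|
| None | 2.26 | 0.72 | 80% | 99% | 88% | >99% |
| 12 | 3.81 | 1.20 | 35% | 78% | 59% | 96% |
| 28 | 4.37 | 1.38 | 22% | 64% | 49% | 94% |
| 78 | 5.10 | 1.61 | 12% | 45% | 37% | 89% |

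At d = 2 with 9 df, power over 78 pairs is 81%. With 8 participants instead of 10 and d = 1 (9 df becomes 7), power is 68% uncorrected, 21% over 12 and 6% over 78.

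**A few individual switches.** Suppose 3 of 10 participants rise by 8 YMRS points, the rest do not change, and the within-group SD is 2 (assumed). In 40,000 simulated samples the paired t-test is significant in 19% with no correction and in fewer than 1% over 12 or more comparisons.

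**MADRS.** Assume SD 8 and correlation 0.5. The SD of change is then 8 × √(2 × (1 − 0.5)) = 8. With a constant 8-point fall at all 12 later ratings, the simulated share of those 12 true changes declared significant is 12% (Bonferroni over 78), about 34% (Bonferroni over 12) and about 47% (Holm over 12). With a 12-point fall, Bonferroni over 78 declares 45%; with a 16-point fall, 81%.

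**The case against.** Much can be said for the plan, and several stronger readings that a reader might draw from it do not hold.

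- **That every pair of visits will be tested.** The text corrects post hoc comparisons without listing them. The 78-pair family is one reading. The pre-specified baseline-to-immediate contrast need not belong to the family at all. This stands, which is why the result is given as a range that starts at 12 comparisons.
- **That the threshold could be as mild as p<0.017.** That figure is 0.05/3, from a model with only Day 0, the immediate visit and 1 month. Such a model has no treatment-day rating, so the figure cannot apply to a rise during treatment.
- **That the corrected comparisons are the only way 9.4 can show a rise.** If treatment-day ratings are in the model, the overall test of time covers them and is not corrected. It can show that something changed, but not at which rating.
- **That a rise is very unlikely to be declared.** This depends on the effect and the degrees of freedom. At 1.5 SD, power over 78 pairs is 45% to 89%.
- **That correction is what hides mania.** With 10 participants, a test of the group mean misses a few individual switches about four times in five even uncorrected. The small sample is the main limit there.
- **That participants are less protected.** The documents do not support this. Sections 5.1, 6.2, 7.1 and 7.2 act on item-level YMRS rises or clinician judgment, and Section 9.2 stops the study on a count of participants above a YMRS score. None of these uses a p-value, and correction alters no estimate.

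On the MADRS, an 8-point fall is modest. Entry requires 20 or more and remission is 10 or less, so any remitter falls by at least 10. Bonferroni is also a valid method, and it yields matching simultaneous intervals directly, which Holm does not. Both points stand and limit the MADRS part.

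**Conclusion.** The point holds in limited form. As written, the Bonferroni rule reaches the YMRS, makes no allowance for its being a harm outcome, and applies to a family that is not defined. Even on the narrowest family that covers the treatment days (12 changes from Day 0), a true mean rise of 1 SD would be declared about 35% of the time at 9 df or 59% at 108 df, against 80% or 88% uncorrected. On the widest family these fall to 12% and 37%.

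These figures rest on alpha of 0.05, complete data from 10 participants and the chosen effect sizes, none of which the plan states. The loss shrinks for larger effects.

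What is at stake is the report: a rise in mean YMRS on a treatment day, or the onset of MADRS improvement, may be labelled not significant in a pilot meant to inform a larger study. Detection of mania in individuals and study stopping are unaffected. In an open-label feasibility pilot this is a change to consider.

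**What to change.** In Section 9.4:

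1. **YMRS.** Report change from Day 0 at each treatment-day, immediate and 1-month rating with an unadjusted 95% confidence interval and no multiplicity correction. Give alongside it the number of participants meeting the protocol's existing YMRS criteria, since a mean can hide a few switches.
2. **MADRS.** Limit post hoc comparisons to change from Day 0, plus immediate against 1 month if wanted, and use Holm in place of Bonferroni. Holm controls the same family-wise error and is never less powerful.
3. State alpha, sidedness and the ratings that enter the model, so that the family can be counted.

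The cost is a few sentences and no new data. There are two drawbacks. Uncorrected YMRS comparisons will raise some false alarms, which is acceptable for a harm outcome if disclosed. Holm does not directly give matching simultaneous intervals; if these are wanted for the MADRS, Bonferroni over the 12 changes from Day 0 still recovers most of the loss relative to 78 pairs (about 34% against 12% in the example above).

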### **3. STUDY DESIGN**

In order to establish feasibility of study design and approach, we will conduct an open label pilot trial of treatment using accelerated iTBS over the left dorsolateral prefrontal cortex (LDLPC) (up to five days, up to 10x/day) using the MagVenture MagPro X100 rTMS System. Participants will have individualized treatment targets that will be produced from structural and functional MRI scans using the software services of Magnus Medical. We will enroll a total of 10 outpatient participants at two participating NNDC centers, the Johns Hopkins University and University of Texas at Austin. The participants will be diagnosed with bipolar I disorder, currently depressed, as determined by a SCID-5 assessment at screening [Day -5/-14]. Participants will be asked to remain on their psychotropic medications for stabilization throughout the screening, baseline, active study and follow-up phases of the study. During active study, changes in medication dosages may be made based on clinical judgment as outlined below. Participants will be required to have an established psychiatrist in order to facilitate ongoing care after the trial.

The expected overall study duration is one year. Each patient will have up to 9 total visits over the course of one month. One visit for consent and screening. One visit for baseline clinical and self-report assessments, MRI scan, and neurocognitive tests. Five consecutive day visits (or less per symptom remission as outlined above via MADRS </=10) of 10 hours each for treatment. Two visits for follow-up. One immediately (up to 5 days) after last day of treatment for clinical and self-report assessments, MRI scan, and neurocognitive tests. And another visit 1-month post-treatment visit for clinical and self-report assessments. All costs for the clinical assessments, MRI scans and TMS treatment related to the conduct of the study will be covered by the study at no expense to the patient. Participants will receive \$500 compensation upon completion of last follow up appointment. This study will offer participants a choice to receive payment/reimbursement through the JHU Greenphire ClinCard Program. The standard Greenphire information sheet will be used to explain the use of Greenphire to participants.

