#### **9.3.2 Secondary Outcomes**

Secondary outcome measures will include changes in MRI derived functional connectivity of the subcallosal cingulate to the DLPFC and within the default mode network. Secondary outcome measures will be assessed as the change between baseline and 1-month post-treatment assessment. Exploratory endpoints include biometrics related to sympathetic nervous system activity - Heart Rate, Sweat Chloride, Body Temperature, and Actigraphy.

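### Section 9.4 analyses the connectivity outcomes as voxel maps, with no single value per outcome and no multiplicity control that reaches those tests

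*Combined protocol and SAP*

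**What the plan says.** Section 9.3.2 defines the secondary outcomes as "changes in MRI derived functional connectivity of the subcallosal cingulate to the DLPFC and within the default mode network". That is two named quantities.

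The second paragraph of Section 9.4 describes the analysis. A seed time series is correlated with "the BOLD time series of each grey matter voxel within the DLPFC or default mode network", each correlation is Fisher-transformed, and then "The resulting connectivity maps will be analyzed with repeated measures ANOVA to compare pre-iTBS vs post-iTBS connectivity measures", with "sex and site as a between-subject covariate". No step averages the voxel values into one number per region. No voxel threshold, cluster rule, family-wise method, false-discovery method or permutation method is given.

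The one multiplicity statement in Section 9.4 is a Bonferroni correction for post hoc pairwise comparisons. It stands in the first paragraph, which deals with the primary clinical outcomes and the biometric endpoints.

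On sample size, Section 3 says "We will enroll a total of 10 outpatient participants at two participating NNDC centers", and Section 9.1 gives the basis: "The sample size for this pilot study was selected to allow for a sufficient evaluation of the feasibility of carrying out the protocol".

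**The concern.** The outcome section promises two answers, while the analysis section produces a map of many. As written, the plan gives no single estimate, and so no single confidence interval, for either named outcome. It also does not say how a voxel or cluster would be judged to have changed. Within the DLPFC and the DMN, the location that ends up being reported can be settled after the map has been seen.

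The stakes are the biomarker findings. Section 1.1 makes change in imaging biomarkers part of the primary objective, and the Abstract and Section 9.1 present the pilot as a source of early data for a larger study. There is no comparison group in which a chance pattern would show itself as chance. If noise voxels define the candidate biomarker, the next study inherits them.

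**Working it through.** **Inputs from the documents.** 10 participants at two sites (Section 3); pre and post scans, with sex and site as between-subject terms (Section 9.4); two named outcomes (Section 9.3.2). The sample size rests on feasibility and the documents give no power calculation, so there is no figure of the plan's own to reproduce.

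**Assumptions, because the documents are silent.** Number of voxels m = 1,000 to 5,000 in total; two-sided alpha of 0.05 or 0.001 per voxel; all 10 participants have both scans; for the simulation, five participants of each sex.

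**Step 1: does the Bonferroni sentence reach these tests?** A pre/post factor has 2 levels, hence 2 × 1 / 2 = 1 pair. There are no post hoc pairs to correct within a voxel, and correcting pairs does nothing about the number of voxels. So it would not help even if it were read across to the imaging paragraph.

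**Step 2: expected false voxels under no change = alpha × m.** This holds whatever the correlation between voxels.
- 0.05 × 1,000 = 50; 0.05 × 5,000 = 250
- 0.001 × 1,000 = 1; 0.001 × 5,000 = 5

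**Step 3: chance of at least one false voxel.** If voxels were independent, it is 1 − (1 − alpha)^m. At 0.05 this is already 99.4% for m = 100. At 0.001 it is 63.2% for m = 1,000 and 99.3% for m = 5,000. Neighbouring voxels are correlated, so this was also simulated: smooth three-dimensional null fields, 10 participants, intercept plus sex plus site, 400 datasets per row.

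| Voxels | Smoothness (FWHM, voxels) | Any p<0.05 | Mean count | Any p<0.001 | Mean count | Any after Bonferroni |
|---|---|---|---|---|---|---|
| 1,000 | 2 | 100% | 50.4 | 59.0% | 1.0 | 6.5% |
| 1,000 | 3 | 100% | 50.7 | 47.5% | 1.1 | 3.5% |
| 1,000 | 4 | 99.75% | 50.8 | 32.25% | 1.0 | 3.0% |
| 4,913 | 2 | 100% | 242.9 | 97.75% | 5.0 | 5.0% |
| 4,913 | 3 | 100% | 244.2 | 93.5% | 4.8 | 4.25% |
| 4,913 | 4 | 100% | 243.4 | 84.25% | 4.9 | 3.5% |

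**Step 4: what the small sample does.** Residual degrees of freedom for the change are 10 − 3 = 7. Each voxel test still has its nominal error rate, so n = 10 does not create false voxels. It does make the obvious correction costly:
- 1,000 voxels: alpha 0.05 / 1,000 = 0.00005, critical |t| = 8.78
- 5,000 voxels: alpha 0.05 / 5,000 = 0.00001, critical |t| = 11.21

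With a noncentral t (noncentrality d√10, 7 df), 80% power at 1,000 voxels needs a mean change of d = 3.34 SD of the change.

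**Step 5: two region values instead.** Two tests at 0.05 give 1 − 0.95² = 9.75% if independent, and at most 0.05 + 0.05 = 10% under any dependence. Holm over the two holds this to 5%. By the same noncentral t, 80% power needs d = 1.03 SD at 0.05 and 1.20 SD at 0.025.

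**The case against.** The best defence is that the plan is silent rather than wrong. It nowhere says that the ANOVA is run voxel by voxel or that results will be read uncorrected, and the imaging team may well intend a standard correction. A reader might infer that the plan declares an uncorrected analysis; the text does not support that. What stands is that a voxel map is the only object the plan hands to the ANOVA, and no rule for judging it is given.

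A reader might also infer that chance findings are certain. That is nearly so at an uncorrected 0.05, but it depends on a threshold the plan never states. At 0.001 the count is a handful, and in some settings most null datasets show none.

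Nor does having 10 participants inflate the error, as Step 4 shows, and adjusting for sex and site does not either. The search is also limited in advance to the DLPFC and the DMN, so any freedom to choose a location lies inside those regions, not across the brain.

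Section 5.1, under Neuroimaging Biomarkers, does plan a region-of-interest analysis with one value per region. It does not close the gap. Those values come from an event-related model of stimulus responses and feed regression analyses, whereas the secondary outcome is resting-state correlation. The two descriptions need reconciling.

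Finally, this is a secondary outcome in an open-label feasibility pilot. That limits the consequence but does not remove it, since passing on candidate biomarkers is one of the pilot's purposes.

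**Conclusion.** The point holds in this form: for the connectivity outcomes, Section 9.4 specifies neither a region-level summary nor any multiplicity control that reaches the imaging tests. On the natural reading of a test at each voxel, and with an assumed 1,000 to 5,000 voxels, no true change would give about 50 to 250 false voxels at an uncorrected 0.05, with at least one almost certain. At an uncorrected 0.001 it would give about 1 to 5, with at least one in roughly 32% to 98% of simulated null datasets, depending on voxel count and smoothness. Voxel count, alpha and smoothness are assumptions.

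The effect is confined to the imaging findings. The MADRS and YMRS analyses are untouched, and nothing here supports a claim that they are compromised. The plan should be changed, because the gap concerns what the secondary outcome is as well as how it is corrected.

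**What to change.** 1. Define each secondary outcome as one prespecified value per participant per scan: (a) mean Fisher-z from the subcallosal cingulate seed over a prespecified DLPFC mask; (b) mean Fisher-z within the DMN over a prespecified seed or set of node pairs. The second needs naming, because Section 9.4 does not say which seed or connections make up the within-network measure.
2. Test the pre-post change in each, keeping the planned sex and site terms, with Holm over the two outcomes. Report each estimate with its 95% confidence interval.
3. State the alpha and name the scan that counts as post. Section 9.3.2 places the secondary outcomes at 1 month, while the schedule in Section 6.1 has MRI only at baseline and immediate follow-up.
4. Keep the voxelwise maps as exploratory, with a named family-wise, cluster or permutation, or false-discovery correction and its threshold. Voxelwise Bonferroni is valid but nearly powerless here.
5. Say how the region-of-interest analysis in Section 5.1 relates to these outcomes.

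The cost is a protocol edit and one averaging step on the same scans. The downside is small: a focal change inside a mask is diluted in the region mean, which is why the corrected maps are worth keeping as exploratory.
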